	Screening/ Baseline	Telephone Visit	Touch up	Telephone Visit		Month 6	Month 12	Optional ^{††} Month 18
Assessment	Day 0*	24h after	Week 3	24h after	Week 6	Week 26	Week 52	Week 76
		IMD admin.)	± 2 days	IMD admin.)	± 5 days	± 7 days	± 7 days	± 7 days
	Visit 1	Visit 1a	Visit 2	Visit 2a	Visit 3	Visit 4	Visit 5	Visit 6
Informed consent	X**							
Eligibility assessment	X**							
Urine pregnancy test ^b	X**				Х	х	Х	х
Demographic data ^a	X**							
Medical history	X**							
Photography	X**				Х	Х	Х	Х
Initial treatment	х							
Touch-up treatment			(x) [†]					
LFS - independent photographic reviewer	х				Х	х	Х	х
LFS - investigator ^c	X**				Х	Х	Х	Х
GAIS - investigator					Х	х	Х	х
GAIS - subject					Х	Х	Х	Х
FACE-Q [™] "Satisfaction with outcome" - subject					Х	Х	Х	Х
FACE-Q [™] "Satisfaction with lips" - subject					Х	Х	Х	Х
Assessment of aesthetic effect - investigator					Х	Х	Х	Х
Pain assessment ^e using the NPRS - subject	х		(x) [†]					
Prior and concomitant medication	X**	х	х	х	Х	х	х	х
Adverse event ^d	X***	x§	X***	x§	Х	х	х	х
Device deficiencies	Х		(x) [†]					

CONFIDENTIAL

- Includes screening and (initial) treatment
- ** Prior to application of the investigational device
- *** In order to identify potential AEs post-administration of IMD, AEs should be assessed 15 minutes after each administration (initial and touch-up treatment).
- [†] Touch-up treatment is optional (at investigator's discretion, if full correction was not achieved after initial treatment).
- The duration of the clinical investigation is planned for 18 months at a maximum and depends on the assessment of the aesthetic effect. In case it is observed by the investigator that no aesthetic effect is any more visible the study can be terminated at Month 12 (Visit 5) for the respective subject.
- Safety follow-up via telephone: Any adverse events since injection? In case of an AE an unscheduled on-site visit should be performed.
- a Includes year of birth, sex, race, and smoking status
- In females of child-bearing potential only, including women who are postmenopausal for less than 12 months
- ^c Evaluated by the investigator using LFS. The upper and lower lip will be graded separately
- To be collected throughout the investigation, beginning immediately after start of initial treatment until the last visit.
- e NPRS: Immediately and 15 minutes after initial and touch-up IMD treatment.

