6.2.2 Methods of use

Prior to administration

 Prior to administration, the subjects should be evaluated for any possible contraindications or risks and should be informed of all possible risks and warnings associated with treatment (also refer to section specified in the IB¹¹).

Preparation for administration

- The skin to be treated should be thoroughly cleaned and disinfected prior to injection of the device and appropriate aseptic technique should be employed throughout the procedure.
- Prior to use the device, the luer-lock adapter should be held securely and the tip cap should be removed by twisting and pulling carefully, which should prevent formation of bubbles. The syringe should be held and the enclosed needle / cannula firmly attached. The needle / cannula should be secured tightly by twisting clockwise. The syringe is held correctly if the backstop opens at the back, toward the hand in which it is held. These steps are illustrated in the Instructions for Use (IFU).

Injection technique

The IMD should be injected into the submucosa of the lips²³. Superficial injections, near the interface of the epidermis and papillary dermis, can result in visible white, yellow, or blue nodules, which may be persistent. Deep injections into the subcutaneous fat may result in loss of the filler in the vast subcutaneous space, requiring larger volumes.

After insertion of the needle / cannula, and just before injection, the plunger rod should be withdrawn slightly to aspirate and verify that the needle is not intravascular.

The 27G $\frac{1}{2}$ " needle or either 25G x 50mm cannula or 22G x 70mm cannula, which are provided with the kit, have to be used. A minimum of 30 subjects will be treated either with 27G $\frac{1}{2}$ " needle or cannula (25G x 50mm or 22G x 70mm cannula).

The technique used is essential for the success of the treatment. The following injection techniques should be employed based on investigator's preference and characteristics of the defect under correction.

These include:

Retrograde technique: introduction of the entire needle / cannula along the wrinkle or skin depression and injecting while slowly withdrawing the needle / cannula.

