6.2.5 Precautions and warnings for the investigator

Refer also to the current IB¹¹ (esp. sections 8.1.5 and 8.1.6) and to the IFU¹⁶:

- The device must only be used by qualified medical healthcare personnel trained on the respective injection technique.
- The device must be injected into non-inflamed, disinfected, healthy skin.
- After use the syringe, needle /cannula and remaining contents should be disposed after use in a special container and the device shall never be re-used.
- The device should not be re-used; quality and sterility can only be guaranteed for a syringe in its original package; Re-use of the device creates potential infection risk for subjects or users.
- Verify the integrity of the syringe and expiry date before use. The device must not be used if the
 expiry date has lapsed, or if the packaging or contents are damaged. Syringes with an open or
 shifted tip cap within the protective packaging must not be used. In such case follow instructions
 given in section 14.8.
- The device should only be used with the syringe, the needle or the additionally provided cannula provided by the manufacturer.
- The needle / cannula must not be manipulated or bent. If the needle / cannula is blocked, do not increase the pressure on the plunger rod but stop the injection and replace the needle. Discard the needle /cannula in a special container
- There are no available clinical data (effectiveness, tolerance) about injecting the device into an area which has already been treated with another filling product.
- The device should not be injected into blood vessels, bones, tendons, ligaments, nerves, muscles
 or naevi. The treating physicians should be familiar with the face's vascular anatomy to avoid the
 incidence of arterial inclusion. During the pretreatment planning phase, proximity of susceptible

vessels to common treatment areas should be considered, being aware that anatomical location of blood vessels can vary between different subjects.

- Overcorrection should be avoided.
- The device should never be placed in contact with quaternary ammonium compounds (such as benzalkonium chloride solutions) or with medical-surgical instruments that have been in contact with these substances.
- The device shall not be used in women who are pregnant or breastfeeding (see section 6.3.7 for more information).
- Subjects should be advised to follow restrictions as given in section 6.3.7.

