6.3.3 Inclusion criteria

A subject must meet **ALL** of the following criteria to be **ELIGIBLE** for the study:

- 1. Adult female or male subjects 18 years of age at Screening/Baseline visit (Visit 1)
- 2. Presence of approximately symmetrical "very thin" lips (minimal red lip shows) to "moderately thick" lips (moderate red lip shows) as assessed with the LFS (severity grade of 1 to 3 on both lips) as determined by the investigator at Visit 1
- 3. For females of childbearing potential only: negative urine pregnancy test at Visit 1, and must agree to use an highly effective method of contraception for the duration of the clinical investigation (see section 6.3.7 for details)
- 4. Healthy skin in the treatment area and free of diseases that could interfere in evaluation of treatment
- 5. Willingness to abstain from any cosmetic or surgical procedures in the treatment area for the duration of the clinical investigation
- 6. Willingness to take part in this clinical investigation documented by a personally signed/dated informed consent.

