6.3.7 Life-style and other restrictions

Contraception

The safety of Saypha® FILLER Lidocaine administration in pregnancy has not been established. Non-clinical studies on reproductive and developmental toxicity of Saypha® FILLER Lidocaine have *not* been conducted. No studies on the effect of Saypha® FILLER Lidocaine on lactation have been conducted. So women of childbearing potential participation should not be pregnant and should use highly effective contraception or avoid unprotected sexual intercourse throughout the clinical investigation. Any pregnancy occurring in study subjects during the investigation (i.e., from date of ICF signature until the last scheduled visit) should be reported as AE and followed-up as described in section 14.

Note 1: A woman is considered to be of childbearing potential (WOCBP) if fertile, following menarche and until becoming postmenopausal unless permanently sterile. Permanent sterilization methods include hysterectomy, bilateral salpingectomy and bilateral oophorectomy. A postmenopausal state is defined as no menses for 12 months without an alternative medical cause.

Note 2: Highly effective methods of birth control include: combined (estrogen and progestogen containing) hormonal contraception associated with inhibition of ovulation (oral, intravaginal, transdermal), progestogen-only hormonal contraception associated with inhibition of ovulation (oral, injectable, implantable), intrauterine device (IUD), intrauterine hormone-releasing system (IUS), bilateral tubal occlusion), vasectomized partner (provided that is the sole sexual partner of the subject and that the vasectomized partner has received medical assessment of the surgical success.) or sexual abstinence (if in line with the preferred and usual lifestyle of the subject and defined as refraining from heterosexual intercourse during the entire period of the trial.

Other restrictions

The following restrictions apply to all subjects:

- Make-up should not be applied for 12 hours after each IMD injection;
- Prolonged exposure to sunlight or ultraviolet (UV) radiation must be avoided for one week after each IMD injection; lip care with UV protection should be used daily throughout the entire clinical investigation;
- To minimise the risk of product mobility, the subject should be advised to avoid massaging the
 treatment site or applying pressure to this area for one week following each IMD injection

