6.5.3 Visit 2 – Week 3 (after Visit 1) ± 2 days

- Record any new AE or changes of AEs (see section 14) with special focus on inflammatory reactions persisting for more than one week or any other occurring secondary effect (see section 6.4.13).
- Record changes in concomitant medication and procedures (see section 6.4.3)

Optional Touch-up IMD administration (see Section 6.2):

The touch-up treatment is optional and will be conducted at investigator's discretion, if full correction was not achieved after initial IMD treatment (i.e., at Visit 1). If the investigator decides to conduct a touch-up treatment, the following assessments must be conducted for the respective subjects:

- Document information on injection (see section 6.4.6)
- Place the one peel-off label of the outer carton box in the subject's medical record (see section 2.5)
- Pain assessment (during treatment) using the NPRS by subject immediately after IMD administration (see section 6.4.8)
- Pain assessment (during recovery from treatment) using the NPRS by subject 15 min after administration of the IMD (see section 6.4.8)
- The subject should be kept at the investigation site and observed for at least 15 min after IMD administration in order to identify potential AEs post-administration
- Re-advise the subject prior to discharge to follow restrictions specified in section 6.3.7 and to
 inform the investigator especially about inflammatory reactions persisting for more than one week
 or any other occurring secondary effect (see section 6.4.13).
- Record any device deficiencies (see section 14.8)

6.5.4 Visit 2a - Telephone Visit - Day 1 (24h after touch-up) – only in case of touch-up treatment

- Ask for any changes in AEs and new AEs (see section 14)
- Ask for changes in concomitant medication and procedures (see section 6.4.3)

In case of an AE an unscheduled on-site visit should be performed (see section 6.5.7).

6.5.5 Visit 3 to 6 – Week 6 to Month 18 (after Visit 1)

Through the follow-up phase of the investigation the following visits will be performed:

- Visit 3 Week 6 (± 5 d) after Visit 1
- Visit 4 Month 6 / Week 26 (± 7 d) after Visit 1
- Visit 5 Month 12 / Week 52 (± 7 d) after Visit 1
- Visit 6 Month 18 / Week 76 (± 7 d) after Visit 1 optional

The following assessment will be performed through these follow-up visits:

- Record any new AE or changes of AEs (see section 14)

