- Record changes in concomitant medication and procedures (see section 6.4.3)
- Women of child-bearing potential: Urine dipstick pregnancy test (see section 6.4.4)
- Lips fullness assessment (LFS) investigator (see section 6.4.7)
- Lips fullness assessment (LFS) independent photographic reviewer; Note: This assessment is performed after the photo has been uploaded (see section 6.4.7).
- GAIS assessment investigator (see section 6.4.8)
- GAIS assessment subject (see section 6.4.8)
- FACE-QTM Satisfaction with overall outcome of treatment (see section 6.4.10)
- FACE-QTM Satisfaction with lips (see section 6.4.11)
- Assessment of aesthetic effect (see section 6.4.12). In case it is observed by the investigator that
 no aesthetic effect is any more visible the study can be terminated at Month 12 (Visit 5) for the
 respective subject; otherwise a visit for optional Month 18 (Visit 6) should be scheduled.

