14.1 Definitions

Adverse Event (AE) is any untoward medical occurrence, unintended disease or injury or untoward clinical sign (including abnormal laboratory findings) in subjects, users or other persons, whether or not related to the IMD.

- For subjects taking part in the clinical investigation this definition includes events related to the procedures involved, as well pregnancy in females.
- For users or other persons this definition is restricted to events related to the IMD.

Adverse Device Effect (ADE): is an AE related to the use of the IMD.

• This includes any AE resulting from insufficiencies or inadequacies in the instructions for use, the deployment, the implantation, the installation, the operation, or any malfunction of the IMD. In addition, this includes any event that is a result of a use error or intentional misuse.

Serious Adverse Event (SAE) is an AE that led to any of the following conditions:

- Death;
- Serious deterioration in the health of the subject that either resulted in:
 - o A life-threatening illness or injury, or
 - o A permanent impairment of a body structure or a body function, or
 - o In-subject or prolonged hospitalization, or
 - Medical or surgical intervention to prevent life-threatening illness or injury or permanent impairment to a body structure or a body function;
- Foetal distress, foetal death, a congenital abnormality or birth defect.

Planned hospitalization for pre-existing condition or a procedure required by the CIP without a serious

Serious Adverse Device Effect (SADE) is an ADE that has resulted in any of the consequences characteristic of an SAE.

Unanticipated Serious Adverse Device Effect (USADE) is defined as an SADE which by its nature, incidence, severity or outcome has not been identified in the current version of the Investigator's Brochure (IB).

Device deficiency is any inadequacy of a medical device with respect to its identity, quality, durability, reliability, safety or performance. This may include malfunctions, use errors, and inadequate labelling.

Device deficiency that might have led to an SAE if a) suitable action had not been taken, or b) intervention had not been made, or c) if circumstances had been less fortunate, is classified as a special type of deficiency and is handled under the SAE reporting system.

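### No pregnancy test is scheduled before the optional Week 3 touch-up, although one gates the Day 0 injection and the device is barred in pregnancy

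*Protocol*

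**What the plan says.** For the first injection, inclusion criterion 3 (CIP section 6.3.3) asks women of childbearing potential for a "negative urine pregnancy test at Visit 1, and must agree to use an highly effective method of contraception". Table 1 marks the test at Visit 1 as done before the device is applied, and section 6.5.1 lists it among the pre-administration assessments.

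For the touch-up, section 6.5.3 says "If the investigator decides to conduct a touch-up treatment, the following assessments must be conducted for the respective subjects". The items listed are the injection details, the carton label, two pain ratings, the 15-minute observation, repeated advice before discharge, and device deficiencies. The general Visit 2 items are adverse events and concomitant treatment. Neither group contains a pregnancy test.

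The "Urine pregnancy test" row of Table 1 is marked at Visits 1, 3, 4, 5 and 6 and is empty at Visits 1a, 2 and 2a. Section 6.4.4 describes the dipstick but sets no timing.

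On use in pregnancy, section 6.2.5 says "The device shall not be used in women who are pregnant or breastfeeding", and section 6.3.7 says that the safety of its "administration in pregnancy has not been established".

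**The concern.** The prohibition in section 6.2.5 covers every use of the device, not only the first. The CIP enforces it by test at Day 0 and then tests again at Visits 3 to 6, where no device is given. It omits the test at the only other visit where the device may be injected.

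A Day 0 result says nothing about a conception after Day 0. A woman of childbearing potential can therefore receive the touch-up without a current test, and a pregnancy that neither she nor the investigator suspects would be exposed to a second injection. Section 6.3.7 adds that no reproductive or developmental toxicity studies were done with this device, so the plan has no data to show that such exposure is harmless.

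**Working it through.** There is no planned figure to reproduce. The check compares the schedule entries and then works out the intervals from the visit windows.

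**Schedule entries (CIP)**

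| Visit | Device injected? | Pregnancy test scheduled? |
|---|---|---|
| 1 (Day 0) | Yes | Yes, before injection |
| 2 (Week 3) | Optional | No |
| 3, 4, 5 and optional 6 | No | Yes |

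Table 1 and section 6.5.3 agree with each other, so the blank cell is not a table-reading fault. Table 1 uses its touch-up mark, (x)†, at Visit 2 for the touch-up itself, the pain assessment and device deficiencies, but not for the pregnancy test. The schedule copied into SAP section 8.1.1 shows no Week 6 column and its marks appear shifted; even read literally, it places no test at Visit 2.

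**Intervals** (windows from Table 1 and section 6.5)

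- Touch-up: 21 ± 2 days = Day 19 to 23. Age of the Day 0 result: 19 to 23 days.
- Next test, Week 6: 42 ± 5 days = Day 37 to 47. Touch-up to next test: 37 − 23 = 14 days at the shortest, 47 − 19 = 28 days at the longest.
- If the Week 6 test were moved to Week 3 instead of a test being added, the next test would be at Month 6: 182 ± 7 days = Day 175 to 189. Touch-up to next test: 175 − 23 = 152 days to 189 − 19 = 170 days.

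**Number of extra tests**

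The documents give neither the touch-up rate nor the share of women of childbearing potential. The ceiling is 110 × 1.00 = 110. If 25% to 50% of the 110 subjects are women of childbearing potential who have a touch-up (an assumption), the range is 110 × 0.25 = 27.5, about 28, to 110 × 0.50 = 55. These are counts of dipsticks, not of pregnancies exposed.

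**Do the other safeguards close the gap?**

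- Contraception is an entry condition, but it applies equally at Day 0 and at Visits 3 to 6, where the CIP still tests.
- Section 6.2.2, reached through the reference to section 6.2 in section 6.5.3, says that "the subjects should be evaluated for any possible contraindications or risks" before administration. It names no test, and it applies at Day 0 as well, where a test is also required.
- Pregnancy counts as an adverse event: section 14.1 says "this definition includes events related to the procedures involved, as well pregnancy in females". Adverse events are elicited by open questions (section 14.2), which cannot reveal a pregnancy that the woman does not know about.
- The repeated advice on section 6.3.7 is listed before discharge, so it need not precede the injection.

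**The case against.** The strongest reply is that the CIP already handles any known or suspected pregnancy. Planned pregnancy and unwillingness to use contraception are exclusions, pregnancy is a reason for withdrawal (section 6.3.5), withdrawal on confirmation is to be immediate (section 14.5), and an unscheduled visit is available on suspicion (section 6.5.7). What remains are unsuspected pregnancies in women who tested negative about three weeks earlier and agreed to highly effective contraception.

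The test can also prevent only part of the exposure. The gel has an anticipated lifetime of up to nine months, so a woman who conceives after Day 0 already carries the first implant. At the 2 mL that the CIP expects may be needed per treatment, the touch-up adds 2 mL × 3 mg/mL = 6 mg of lidocaine, with a half-life of around 90 minutes. Unestablished safety is an absence of data, not a known harm. The CIP also cites no rule that requires a test before each injection, and the change needs an amendment.

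Most of this stands as a limit on the size of the problem. It does not remove the gap: every provision listed acts on a known or suspected pregnancy, and the later tests come after the injection. The argument for the test is internal consistency, since the CIP did not accept the same safeguards as sufficient before the first injection.

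**Conclusion.** The gap is real and minor. The CIP requires a negative pregnancy test before one of its two permitted injections and none before the other, while barring use in pregnancy for both. At touch-up the last scheduled result is 19 to 23 days old, and the next comes 14 to 28 days too late to prevent exposure. The added harm is limited to one further injection in an unrecognised pregnancy. How often that would happen cannot be derived from the documents, and existing safeguards make it less likely. The primary endpoint, sample size and analyses are unaffected; pregnancy tests are only listed (CIP section 7.3.8, SAP section 10.7.3). The interval figures rest only on the stated visit windows; the 28 to 55 range rests on an assumed share.

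**What to change.** In Table 1, put (x)† in the pregnancy-test row at Visit 2. In section 6.5.3, add a first touch-up item, before the injection: for women of childbearing potential, a urine dipstick as described in section 6.4.4, with touch-up given only if the result is negative. Keep the Week 6 and later tests, which monitor pregnancy during the study; moving the Week 6 test forward would open the 152 to 170 day interval shown above.

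The cost is one dipstick per touch-up subject of childbearing potential: at most 110, or about 28 to 55 under the stated assumption. Each such woman already has four scheduled tests, or five with the optional Visit 6. The change also needs one eCRF field and a written amendment with additional written consent from affected subjects, as CIP section 9 requires when procedures change. It can apply only to touch-ups not yet given.

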6.4.12 Assessment of aesthetic effect

At each follow-up visit, the investigator will evaluate the aesthetic effect. The presence of an aesthetic effect at a given visit relative to baseline will be recorded as either "YES" or "NO" in the subject's medical record and in the eCRF.

The duration of the clinical investigation is planned for 18 months at a maximum and depends on the assessment of the aesthetic effect. In case it is observed by the investigator that no aesthetic effect is any more visible the study can be terminated at Month 12 (Visit 5) for the respective subject.

If no aesthetic effect is present anymore new injections for lip augmentation might be placed at previously injected locations after 3 months in general.

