7.5 Missing data

Adverse events with unknown onset times will be counted as post IMD administration AEs. AEs with missing relationship to IMD will be counted as related AEs (ADEs).

In addition, there will be no imputation of missing values. All data will be analyzed as they appear in the data base.

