9.1 Descriptive Statistics

The following descriptive statistics will be calculated for continuous data and for ordered categorical data (ordinal data):

Summary statistics are displayed with the following digits:

Description	Characteristic	Number of decimal places
Count	n	0
Count corresponding to the number of subjects for a group	N	0
Mean	Mean	As in source + 1
Standard Deviation	SD	Mean+1
Minimum	Min	As in source
Median	Median	As in source + 1
Maximum	Max	As in source
Quartile 1	Q1	As in source+1
Quartile 3	Q3	As in source+1
Percentage relative to N #	%	1

Number of decimal places can be more than one, if necessary. All table percentages should be rounded to one decimal place if not stated otherwise.

All data will be presented in the subject data listings.

If either table or listing does not include any observation, then the following placeholder will be used: "NO SUBJECTS MET THE CONDITION FOR INCLUSION".

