9.5.2 Other Specifications

Summaries will be based on scheduled time points.
 In general, subject data listings should include all dosed subjects with data. However, if a subject data listing includes only subjects who met a certain condition, i.e., subjects with serious adverse events, and there are no subjects who met that condition, then a page marker will appear indicating that “No subjects met the condition for inclusion.”

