The extent of subject's satisfaction with overall outcome of the treatment, at Week 6, Month 6, 12 and optional Month 18 after initial treatment, assessed by the subject using the Face-Q™ Questionnaire "Satisfaction with Outcome" for each question will be summarized by number and percentage using PPS and FAS population.

Face Q data will be analyzed according to the FaceQ USER'S GUIDE (VERSION 1.0 January 2015). The raw summed scale score is converted to a score from 0 to 100 by using the respective Conversion Tables available from the authors. Higher scores reflect a better outcome (i.e., 0 (worst) to 100 (best)).

Listings will be provided for Face-Q™ Questionnaire "Satisfaction with Outcome".

6. The extent of subject's satisfaction with augmentation of lips, at Week 6, Month 6, 12 and optional Month 18 after initial treatment, assessed by the subject using the Face-Q™ Questionnaire "Satisfaction with Lips".

The extent of subject's satisfaction with augmentation of lips, at Week 6, Month 6, 12 and optional Month 18 after initial treatment, assessed by the subject using the Face-Q™ Questionnaire "Satisfaction with Lips" for each question will be summarized by number and percentage using PPS and FAS population.

Listings will be provided for Face-Q™ Questionnaire "Satisfaction with Lips".

7. Subject's perception of pain after initial and touch-up treatment with Saypha® FILLER Lidocaine using the 11-point Numeric Pain Rating Scale (NPRS), where 0 is no pain and 10 is the worst pain imaginable.

Subject's perception of pain after initial and touch-up treatment with Saypha® FILLER Lidocaine using the 11-point Numeric Pain Rating Scale (NPRS) will be analyzed descriptively using PPS and FAS populations.

Paired t-test will be performed to check the mean difference between "immediately after" and "15 minutes later at each visit are significant at 5% level of significance.

Listings will be provided for Numeric Pain Rating Scale (NPRS).

8. Percentage of subjects demonstrating an aesthetic effect at Week 6, Month 6, 12 and optional Month 18 based on the investigator's life assessment.

Percentage of subjects demonstrating an aesthetic effect at Week 6, Month 6, 12 and optional Month 18 based on the investigator's life assessment will be summarized by number and percentage using PPS and FAS population.

	Statistical Analysis Plan Sponsor: CROMA-PHARMA GmbH
	Study Number: CPH-101-201479 Version: Final 1.0 Date: 07 Jun 2021

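### Month 18 attendance can depend on the Month 12 aesthetic-effect rating, but the SAP fixes neither the Month 18 denominator nor how subjects ended at Visit 5 are counted

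*Protocol*

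**What the plan says.** Protocol section 6.4.12 has the investigator rate the aesthetic effect at every follow-up visit: "The presence of an aesthetic effect at a given visit relative to baseline will be recorded as either" YES or NO, in the medical record and the eCRF. The same section says that if "no aesthetic effect is any more visible the study can be terminated at Month 12 (Visit 5) for the respective subject". Section 6.5.5 repeats this and adds "respective subject; otherwise a visit for optional Month 18 (Visit 6) should be scheduled". The footnotes to the SAP's schedule of procedures carry the termination rule over.

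That rating is secondary endpoint 8 in SAP 10.6.2: "Percentage of subjects demonstrating an aesthetic effect at Week 6, Month 6, 12 and optional Month 18", to be given as number and percentage in the PPS and FAS. The section does not say which subjects form the percentage base at Month 18.

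Three general statements bear on it:
- Protocol 7.5: "In addition, there will be no imputation of missing values. All data will be analyzed as they appear in the data base".
- SAP 9.5.2: "Summaries will be based on scheduled time points".
- SAP 9.1, in the table of decimal places: "Percentage relative to N", where N is the "Count corresponding to the number of subjects for a group".

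None mentions Month 18 or subjects ended at Visit 5. SAP 9.5.1 covers FACE-Q items, adverse event and medication dates, and missing adverse event relationship or intensity. The only sensitivity analysis (SAP 10.9) concerns the site effect on the primary endpoint. SAP 10.1 tabulates subjects by visit and withdrawals with reasons, with no row for subjects ended at Visit 5 because the effect had gone.

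**The concern.** For endpoint 8 this is selection on the outcome and differs from ordinary dropout: a NO at Month 12 can remove the subject from the Month 18 assessment of the same rating. The first two general statements suggest a base of Month 18 attendees. The third suggests the whole analysis set. On the first reading, subjects whose effect has already gone leave the denominator and persistence looks better than it was. On the second they stay in, but so does anyone lost while still showing an effect, who then counts as a failure. Neither reading separates an effect that has gone from an effect that was not observed.

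Duration of the aesthetic effect is one of two main objectives (protocol 5.1, SAP 7.1.1), and Month 18 is its last time point. The protocol anticipates a lifetime of up to nine months (sections 2.1 and 4.1), so NO ratings at Month 12 are foreseeable, although no share is given.

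**Working it through.** **The plan's own figures.** Protocol 7.1 and SAP 9.6 give 95% half-widths for a 0.90 responder rate. 1.96 × √(0.9 × 0.1/n) is 0.0588 at n=100 and 0.0832 at n=50, matching 0.059 and 0.083; 100 × 1.10 = 110 enrolled. All of this concerns Week 6. The plan states no Month 18 figure.

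**Inputs, all assumed because the documents give none:**
- q: share with an effect at Month 12
- t: share of no-effect subjects ended at Visit 5
- k: share of those with an effect at Month 12 who keep it to Month 18
- m: share of no-effect subjects who would be rated YES at Month 18; at first m=0
- Other losses are taken as unrelated to effect.

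**Attendee-only base.** The rate in everyone is qk. The share attending is q+(1-q)(1-t), so the attendee rate is qk/[q+(1-q)(1-t)]. The overstatement factor is 1/[q+(1-q)(1-t)]; k cancels.

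| q | t=0 | t=0.5 | t=1 |
|---|---|---|---|
| 0.9 | 1 | 1/0.95 = 1.05 | 1/0.90 = 1.11 |
| 0.8 | 1 | 1/0.90 = 1.11 | 1/0.80 = 1.25 |
| 0.6 | 1 | 1/0.80 = 1.25 | 1/0.60 = 1.67 |
| 0.4 | 1 | 1/0.70 = 1.43 | 1/0.40 = 2.50 |

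With k=0.5, as an illustration:
- q=0.9: true rate 45%, attendee rate 47.4% (t=0.5) to 50% (t=1)
- q=0.6: true rate 30%, attendee rate 37.5% to 50%
- q=0.4: true rate 20%, attendee rate 28.6% to 50%

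**Relaxing m=0.** At t=1 the attendee rate is k and the true rate is qk+(1-q)m. With q=0.6 and k=0.5:
- m=0.05: 0.30+0.02 = 0.32, factor 0.50/0.32 = 1.56
- m=0.10: 0.30+0.04 = 0.34, factor 0.50/0.34 = 1.47

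The factors in the table are therefore upper bounds if m > 0. At t=1 the attendee rate is right only if m=k, that is, if ended subjects would be rated YES as often as those who still had an effect at Month 12.

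**Whole-FAS base.** Let N be the FAS, L the subjects lost after entering it for reasons other than a NO rating, and x those rated YES at Month 18. The whole-FAS rate is x/N and the rate among those of known status is x/(N-L), so the ratio is 1-L/N. There is no overstatement. The understatement equals the Month 18 loss rate, which the documents do not give.

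**The case against.** The strongest case against runs as follows.

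- *Month 18 is optional and endpoint 8 is descriptive and secondary.* Protocol 3.3 presents the extended follow-up as additional long-term information, and with a lifetime of up to nine months the key duration data are at Months 6 and 12. This stands and limits the severity. A descriptive percentage still needs a defined base.
- *Ending at Visit 5 is permissive.* True, and t=0 gives no bias. Discretion also means that t may differ between investigators.
- *The tables already let a reader see it.* Item 8 gives counts at Month 12 and Month 18, SAP 10.1 gives subjects by visit, and all data are listed. This partly stands: the size of the gap will be visible. No planned table shows whether those absent at Month 18 are those rated NO at Month 12.
- *Early-termination assessments fill the gap.* Protocol 6.3.5 and 6.5.6 ask for Visit 6 assessments at withdrawal. But protocol 6.4.3 and 6.4.13 allow Visit 5 as the final visit, so these exits read as completion. Even if such assessments were done, they would date from Month 12, and the SAP has no rule carrying them to Month 18.
- *Re-treatment is covered.* Partly so: subjects agree to abstain from procedures in the treated area, additional correction is a withdrawal reason, and procedures are recorded at each visit. None of this sets the Month 18 count.
- *Counting exits as no effect is single-value imputation.* Correct, and contrary to protocol 7.5 as written. It needs a stated exception and assumption, with the attendee-only rate beside it.

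**Conclusion.** The gap is real and its severity is minor to moderate. If attendees are the base, the Month 18 rate for endpoint 8 is too high by the factors shown, given m=0 and assumed values of q and t. It is unbiased if nobody is ended at Visit 5, and the factors are upper bounds if some ended subjects would regain a YES. If the whole FAS is the base, that overstatement disappears but losses count as failures, by an amount that cannot be stated from the documents. Week 6, Month 6 and Month 12 results are not affected.

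Three stronger readings are tempting and are not supported:
- A reader might infer a whole-FAS dilution of 100/110 = 0.91 from the enrolment allowance. That allowance is tied to the Week 6 estimate. FAS entry requires a post-treatment LFS, first scheduled at Week 6, so subjects lost before then are generally outside the FAS.
- A reader might infer that the plan prescribes an attendee-only analysis at Month 18. It leaves both bases open, for LFS and GAIS as well as for endpoint 8.
- A reader might carry the same factors over to LFS or GAIS. The YES/NO rating is not the same as a change of less than one LFS grade, so the size of any effect there is unknown.

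**What to change.** Amend SAP 10.6.2 item 8, add a row to SAP section 11, and handle the exception to protocol 7.5 under protocol 7.7:

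- (a) Set the Month 18 denominator to Month 18 attendees plus subjects rated NO at Visit 5 who have no Visit 6. The flag can be derived from the eCRF rating.
- (b) Count the latter as no effect at Month 18, and state the assumption that a lost effect does not return without new treatment.
- (c) Treat all other absences as missing and report their number.
- (d) Show the attendee-only rate beside it, labelled as such.

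For Month 18 LFS, GAIS and FACE-Q, including LFS and GAIS by manufacturing site (SAP 10.8), state that the denominator is subjects assessed at Month 18 and label the tables accordingly. In SAP 10.1 add a row for subjects ended at Visit 5 with no aesthetic effect, separate from dropouts. The clinical rule on ending subjects at Visit 5 is left as it is.

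The cost is one derived flag, one disposition row, one extra table line and some labels, with no new visits or assessments. Protocol 7.7 asks for a protocol amendment where the effectiveness analysis is affected, so one should be planned. The Month 18 figure may look less favourable than the attendee-only rate.
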